**Table 2. Treatment Interruptions and Restart**

Toxicity	Grade	Instructions for Treatment Interruptions and Restart
Cytokine release syndrome (continued)	Grade 4	
 
• Permanently discontinue blinatumomab if:               
 
○ Initial grade 3 CRS does not improve to <math>\leq</math> grade 1 within 7 days, OR
 
○ Grade 3 CRS reoccurs at the lower dose level within 7 days of re-initiation, OR
 
○ Grade 3 CRS reoccurs at a dose of 9 <math>\mu</math>g/day cIV (or the equivalent SC dose) without prior step-dose escalation
 
 
 
 <hr/> 
 
• Permanently discontinue blinatumomab
 

Elevated liver enzymes		
 
• Interrupt blinatumomab if any 1 of the following occurs:               
 
○ TBL > 3 <math>\times</math> ULN at any time
 
○ ALP > 8 <math>\times</math> ULN at any time
 
○ AST or ALT > 8 <math>\times</math> ULN at any time
 
○ AST or ALT > 5 <math>\times</math> ULN but < 8 <math>\times</math> ULN for <math>\geq</math> 2 weeks
 
○ AST or ALT > 3 <math>\times</math> ULN with clinical signs or symptoms that are consistent with hepatitis (eg, RUQ abdominal pain/tenderness, fever, nausea, vomiting, jaundice)
 
 
 
• Permanently discontinue blinatumomab if:               
 
○ TBL > 2 <math>\times</math> ULN OR INR > 1.5 (for subjects not on anticoagulant therapy)
 
 
AND
 
 
○ AST or ALT > 3 <math>\times</math> ULN (when baseline was < ULN)
 
 
AND
 
 
○ No other cause for the combination of the above laboratory abnormalities is immediately apparent
 
 
Refer to Section 6.3 for additional details
 
 

Other clinically relevant adverse events	Grade 3	
 
○ Interrupt blinatumomab until <math>\leq</math> grade 1
 
○ Restart no less than 72 hours after the initial observation of the grade 3 event at the following dose levels:
 
 
For cIV infusion
 
 
○ If event occurred at 112 <math>\mu</math>g/day, resume cIV infusion at 28 <math>\mu</math>g/day
 
○ If event occurred at dose of 9 <math>\mu</math>g/day or 28 <math>\mu</math>g/day, resume cIV infusion at 9 <math>\mu</math>g/day
 
○ Escalate up 1 dose level after 7 days if toxicity does not reoccur. Increase dose stepwise at 7-day intervals to target dose of 112 <math>\mu</math>g/day if toxicity does not re-occur
 

Approved

Abbreviations defined on last page of the table.

**Table 2. Treatment Interruptions and Restart**

Toxicity	Grade	Instructions for Treatment Interruptions and Restart
Other clinically relevant adverse events (continued)	Grade 3	
For SC week 4 Period 1/Cycle 1
 
 
○ Resume at 28 µg/day cIV infusion.
 
○ Escalate up after 7 days if toxicity does not reoccur to 112 µg/day cIV infusion for 7 days.
 
○ Hold cIV infusion for 12 hours if toxicity did not reoccur
 
○ Resume with the day SC that toxicity occurred at the dose of that cohort (i.e if toxicity occurred on day 23 then resume SC on day 23 of cycle and repeat all labs that are written for this day on Schedule of Assessments).
 
 
For SC Period 2:
 
 
○ If event occurred at MTD SC, resume SC at 28 µg/day equivalent SC
 
○ If event occurred at 28 µg/day SC equivalent, resume SC at 9 µg/day SC equivalent
 
○ Escalate up 1 dose level after 7 days if toxicity does not reoccur. Increase dose stepwise at 7-day intervals to MTD SC
 
 
 
● Permanently discontinue blinatumomab if:               
 
○ Initial grade 3 event does not improve to grade ≤ 1 within 14 days, OR
 
○ Grade 3 event reoccurs at the lower dose level within 7 days of re-initiation, OR
 
○ Grade 3 event reoccurs at a dose of 9 µg/day cIV (or the equivalent SC dose) without prior step-dose escalation
 
 
 

	Grade 4	Permanently discontinue for non-laboratory adverse events at least possibly related to blinatumomab

Page 4 of 4

Abbreviations: ALP = alkaline phosphatase; ALT = alanine aminotransferase; AST = aspartate aminotransferase; cIV = continuous intravenous; CRS = cytokine release syndrome; INR = international normalized ratio; MRI = magnetic resonance imaging; **MTD = maximum tolerated dose**; RUQ = right upper quadrant; SC = subcutaneous; TBL = total bilirubin level; ULN = upper limit of normal.

Biomarker samples, as described in [Section 7.5](#), will also be collected for grade ≥ 3 neurologic adverse events or grade ≥ 3 CRS that occur in all periods of the study at the start of the adverse event and at the time of resolution of the adverse event.

**If ≥ 2 subjects within any Cycle1/Period 1 cohort experience a DLT, the remaining subjects enrolled in that cohort that have not reached the SC week 4 of Cycle 1/Period 1 will not receive any SC but can continue on cIV dosing to complete 6 weeks of IV treatment.**

Approved

#### 6.2.1.4.3 Criteria for Permanent Discontinuation of Blinatumomab

Treatment with blinatumomab should be permanently discontinued in the event of any of the following (see [Section 8.3.1](#)):

- clinically relevant disease progression, relapse, non-response **for subjects in period 1**
- subject or investigator not compliant with the study protocol
- administration of relevant non-permitted concomitant medication(s)
- occurrence of an adverse event which makes discontinuation from treatment necessary due to protocol specified safety criteria or desirable in the investigator's and/or the subject's opinion
- occurrence of one of the following (defined in [Appendix E](#)):
  - a second seizure that occurred with re-initiation of blinatumomab at any dose
  - a CTCAE grade 4 neurologic event
  - an initial grade 3 neurologic event that does not improve to  $\leq$  grade 1 within 7 days
  - a grade 3 neurologic event that reoccurs at the lower dose level within 7 days of re-initiation
  - **Initial grade 3 neurologic event that occurred at the 9  $\mu\text{g}/\text{day}$  cIV or 9  $\mu\text{g}/\text{day}$  SC equivalent without prior dose escalation**
  - grade 4 CRS
- grade 3 CRS that reoccurs at the lower dose level within 7 days of re-initiation
- initial grade 3 CRS that does not resolve to  $\leq$  grade 1 within 7 days
- grade 3 CRS that reoccurs at a dose of 9  $\mu\text{g}/\text{day}$  cIV (or the equivalent SC dose) without prior step-dose escalation
- elevated liver enzymes (meeting all of the criteria below):
  - total bilirubin (TBL)  $> 2 \times$  ULN or international normalized ratio (INR)  $> 1.5$  (for subjects not on anticoagulant therapy)
  - AST or ALT  $> 3 \times$  ULN (when baseline was  $<$  ULN)
  - no other cause for the combination of the above laboratory abnormalities is immediately apparent
- an infusion interruption of more than 14 days due to an adverse event related to blinatumomab (with the exception of delay in restart due to logistical difficulties, in which case the restart may be postponed for an additional 7 days)
- any grade 4 non-laboratory adverse event at least possibly related to blinatumomab

#### 6.3 Hepatotoxicity Stopping and Rechallenge Rules

Subjects with abnormal hepatic laboratory values (ie, alkaline phosphatase [ALP], AST, ALT, TBL) and/or INR and/or signs/symptoms of hepatitis (as described below) may meet the criteria for withholding or permanent discontinuation of Amgen investigational

product or other protocol-required therapies as specified in the Guidance for Industry Drug-Induced Liver Injury: Premarketing Clinical Evaluation, July 2009.

### 6.3.1 Criteria for Permanent Discontinuation of Blinatumomab and Other Protocol-required Therapies Due to Potential Hepatotoxicity

Blinatumomab and other protocol-required therapies should be discontinued permanently and the subject should be followed according to the recommendations in [Appendix D](#) (Additional Safety Assessment Information) for possible drug induced liver injury (DILI), if ALL of the criteria below are met:

- TBL > 2 × ULN or INR > 1.5
- AND increased AST or ALT from the relevant baseline value as specified below:

Baseline AST or ALT value	AST or ALT elevation
< ULN	> 3 × ULN

- AND no other cause for the combination of the above laboratory abnormalities is immediately apparent; important alternative causes for elevated AST/ALT and/or TBL values include, but are not limited to:
  - hepatobiliary tract disease
  - viral hepatitis (eg, Hepatitis A/B/C/D/E, Epstein-Barr Virus, cytomegalovirus, Herpes Simplex Virus, Varicella, toxoplasmosis, and Parvovirus)
  - right sided heart failure, hypotension or any cause of hypoxia to the liver causing ischemia
  - exposure to hepatotoxic agents/drugs or hepatotoxins, including herbal and dietary supplements, plants and mushrooms
  - heritable disorders causing impaired glucuronidation (eg, Gilbert's Syndrome, Crigler-Najjar syndrome) and drugs that inhibit bilirubin glucuronidation (eg, indinavir, atazanavir)
  - alpha-one antitrypsin deficiency
  - alcoholic hepatitis
  - autoimmune hepatitis
  - Wilson's disease and hemochromatosis
  - nonalcoholic Fatty Liver Disease including Steatohepatitis (NASH)
  - non-hepatic causes (eg, rhabdomyolysis, hemolysis)
  - cytokine release syndrome

If an alternative cause for hepatotoxicity is identified or less stringent conditions developed than what are noted above, the investigator should determine (based on patient population and/or severity of the hepatotoxicity or event) if blinatumomab and

Approved

other protocol-required therapies should be withheld or permanently discontinued, as deemed appropriate for the safety of the subject.

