### 4.1 Inclusion and Exclusion Criteria

#### 4.1.1 Inclusion Criteria

101. Subject has provided informed consent
102. Age  $\geq$  18 years old at the time of informed consent
103. Subjects must have a histologically determined B cell NHL subtype as defined in the bullets below. In addition, they must have disease that is primary refractory after initial therapy or have relapsed disease.
  - Follicular Lymphoma I, II, IIIA
  - Marginal zone lymphoma (extranodal, nodal, or splenic). Subjects with gastric mucosa-associated lymphoid tissue must have progressed after *Helicobacter pylori* therapy and radiation. Subjects with splenic marginal zone lymphoma must have prior splenectomy.
  - Lymphoplasmocytic lymphoma
  - Mantle cell lymphoma ([MCL] with the exception of aggressive MCL, defined as Ki67 > 30%, or blastoid histology)
  - Small lymphocytic lymphoma

104. Subjects without standard therapy alternatives, or contraindicated for standard therapy by investigator, or subjects unwilling to receive standard therapy. The disease status must be 1 of the following:
  - primary refractory (at least 1 prior line of therapy)
  - relapsed within 1 year of first response
  - responded to initial therapy for  $\geq 1$  year and relapsed after 2 or more lines of therapy, including an anti-CD20 monoclonal antibody
105. Measurable disease that has not been previously irradiated on positron emission tomography–computed tomography (PET-CT), or computed tomography (CT), of at least 1.5 cm within the last 21 days before the start of IP treatment.
106. Eastern Cooperative Oncology Group (ECOG) performance status  $\leq 2$  ([Appendix C](#)).
107. Life expectancy  $\geq 3$  months as determined by the treating physician.
108. Subjects must have adequate organ and bone marrow function at screening as defined below:
  - Hematological:
    - peripheral neutrophils  $> 500/\mu\text{L}$  prior to start of treatment
    - hemoglobin  $\geq 8$  g/dL
    - platelets  $\geq 50,000/\mu\text{L}$
  - Hepatic:
    - aspartate aminotransferase (AST)/Alanine aminotransferase (ALT)  $< 5 \times$  upper limit of normal (ULN)
    - total bilirubin  $\leq 1.5 \times$  ULN
  - Renal:
    - creatinine clearance  $\geq 50$  mL/min (Cockcroft-Gault)

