#### 6.2.1.2.2 Dose Limiting Toxicity Rules

##### Cycle 1/Period 1

The DLT evaluation period includes the entire **week 4 (7 days) which is the week that blinatumomab is administered** SC during Cycle 1/Period 1 of the study. To be evaluable for a DLT, subjects must have experienced a DLT within the DLT evaluation period. In addition, if the investigator and/or sponsor removes the subject from the study due to a treatment-related toxicity during the DLT evaluation period, regardless of the grade of toxicity, this will be considered a DLT. If a subject does not experience a DLT during the DLT evaluation period and does not receive **all doses (q48h, q72h, q96h, or q7d dosing)**, at least 4 of the 5 doses (q24h dosing), or at least 8 of 9 doses (q12h dosing) of **SC** blinatumomab during Cycle 1/Period 1 of the study, the subject will not be considered DLT-evaluable and will be replaced as described in [Section 3.4.1](#).

If  $\leq 1$  of the 6 evaluable subjects in a dose SC cohort experience a DLT during the SC administration, then the dose will be determined to be tolerable and the next dose-cohort level will be initiated in a new dose-cohort of subjects after review by the DLRT.

If  $\geq 2$  subjects of the 6 evaluable subjects in a SC dose cohort experience a DLT during SC administration then dosing will stop for individual subjects who experience a DLT, a DLRT meeting will be conducted, and further steps will be determined.

Additionally, the DLRT will meet:

- once dose-cohort 1 has completed subcutaneous dosing
- once dose-cohorts 2 and 3 have completed subcutaneous dosing
- once any additional cohorts complete dosing if additional dose-cohorts are tested to determine the MTD in Cycle 1/Period 1

## Cycle 1/Period 2

For subjects who receive optional Cycle 2 after Cycle 1/Period 2 (SC dosing period), the DLT evaluation period includes the entire duration of SC administration **in Cycle 1** and 16 days following the last SC dose (56 days in total) or until the start of optional Cycle 2, whichever is longer, up to 30 days after the last SC dose **of Cycle 1**.

For subjects who do not receive optional Cycle 2, the DLT evaluation period includes the entire duration of SC administration and 30 days following the last SC dose (70 days in total).

Continuous monitoring for early termination of the trial will be performed (refer to [Section 10.2](#)).

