### 6.3.3 Criteria for Rechallenge of Blinatumomab and Other Protocol-required Therapies After Potential Hepatotoxicity

If signs or symptoms recur with rechallenge, then blinatumomab and other protocol-required therapies, as appropriate, should be permanently discontinued.

Subjects who clearly meet the criteria for permanent discontinuation (as described in [Section 6.2.1.4.3](#)) should never be rechallenged.

Approved

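### The hepatic permanent-stop rule has no row for a rising AST or ALT that was already at or above ULN at baseline, although inclusion 108 admits values up to 5 × ULN

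*Protocol*

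**What the plan says.** **Entry.** The hepatic line of inclusion criterion 108, which begins "aspartate aminotransferase (AST)/Alanine aminotransferase (ALT", sets the limit at below 5 × ULN. Total bilirubin must be no more than 1.5 × ULN.

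**Permanent stop.** The rule appears three times.
- Section 6.3.1 needs all of: TBL above 2 × ULN or INR above 1.5; "AND increased AST or ALT from the relevant baseline value as specified below"; and no other cause immediately apparent. Its table has one row: baseline below ULN, elevation above 3 × ULN.
- Table 2 sets the enzyme limb at more than 3 × "ULN (when baseline was" below ULN).
- Section 6.2.1.4.3 lists "elevated liver enzymes (meeting all of the criteria below" and repeats the restriction.

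Under Section 6.3.3, "Subjects who clearly meet the criteria for permanent discontinuation" are never rechallenged.

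**Withholding.** Section 6.3.2 applies at any baseline. Its triggers are AST or ALT above 8 × ULN; between 5 and 8 × ULN for at least 2 weeks, or when enhanced monitoring is not possible; above 3 × ULN with hepatitis symptoms; TBL above 3 × ULN; or ALP above 8 × ULN. The Table 2 interruption list is the same except for the monitoring item. Neither uses INR.

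**Discretion.** Section 6.3.1 ends: "If an alternative cause for hepatotoxicity is identified or less stringent conditions developed than what are noted above, the investigator should determine" whether treatment is withheld or permanently stopped. Section 6.2.1.4.3 also lists "occurrence of an adverse event which makes discontinuation from treatment necessary due to protocol specified safety criteria or desirable in the" opinion of the investigator or the subject.

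**The concern.** Section 6.3.1 speaks of the relevant baseline value, as if several baseline classes would follow, and then gives only one. Section 6.3.2 expects subjects with abnormal baseline transaminases, and the introduction to Section 6.3 names INR among the findings that may lead to withholding or stopping. For a raised baseline, though, the combined signal of transaminase rise plus raised bilirubin or INR appears in no numeric rule.

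The sponsor made that combination, without another cause, a mandatory stop. It did not leave it to judgement when the baseline was normal. For eligible subjects who start at or above ULN, the same laboratory picture carries no automatic action, and the bar on rechallenge in Section 6.3.3 is not reached through this criterion.

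**Working it through.** The plan gives no figure to reproduce here. The check applies the written rules to eligible baselines.

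**Rules** (enzymes, TBL and ALP in multiples of ULN; AST and ALT taken separately because the text says AST or ALT)
- Stop: (TBL > 2 or INR > 1.5), and at least one enzyme with baseline < 1 and current value > 3, and no other cause.
- Hold: any enzyme > 8; or > 5 and < 8 for ≥ 2 weeks or without enhanced monitoring; or > 3 with symptoms; or TBL > 3; or ALP > 8.

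**Assumptions.** No symptoms, ALP not above 8 × ULN, not on anticoagulants, enhanced monitoring possible, no other cause. The entry value is taken as the hepatic baseline. Criterion 108 applies at screening and SAP Section 6 defines baseline as day 1, so the two could differ.

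| Baseline AST / ALT | On treatment | Result |
|---|---|---|
| 0.9 / 0.9 | ALT 4, INR 1.8 | Stop |
| 1.2 / 0.9 | ALT 4, INR 1.8 | Stop, through ALT |
| 1.2 / 0.9 | AST 4, ALT 2.5, INR 1.8 or TBL 2.5 | No numeric trigger |
| 1.2 / 1.2 | Both 4, INR 1.8 or TBL 2.5 | No numeric trigger |
| 1.2 / 1.2 | Both 7 for 1 week, INR 1.8 | No numeric trigger |
| 1.2 / 1.2 | Both 7 for 2 weeks, INR 1.8 | Hold |
| 1.2 / 1.2 | Both 8.1, INR 1.8 | Hold |
| 1.2 / 1.2 | Both 4, TBL 3.1 | Hold |
| 1.5 / 1.5 | Both 20, TBL 10, INR 3 | Hold only; from baseline 0.9, stop |

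The uncovered region is therefore: rising enzyme at or above ULN at baseline; AST/ALT above 3 to 5 × ULN, or above 5 and below 8 × ULN for under 2 weeks with monitoring possible; and TBL above 2 to 3 × ULN or INR above 1.5. Entry TBL is at most 1.5 × ULN, so a TBL above 2 × ULN is always a rise from entry.

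**The DLT route.** Section 8.3.1 makes a DLT within the evaluation period a reason for removal from treatment. Under Section 6.2.1.2.3, related grade 3–4 laboratory abnormalities count unless they resolve to grade 1 or less within 7 days. In Period 1 the window is "week 4 (7 days) which is the week that blinatumomab is administered" SC.
- Period 1, cycle 1: 7 / 42 treatment days = 17%.
- Period 1 with optional Cycle 2: 7 / 84 = 8%.
- Period 2: all of cycle 1 and a follow-up interval. The window is defined on cycle 1, not on optional Cycle 2.

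The documents do not print the CTCAE cut-offs. If the grade 3 transaminase cut-off lies anywhere from 3 to 8 × ULN (assumption), transaminases alone could make the 4 × ULN cases a DLT only if the cut-off is below 4, and the 7 × ULN case only if it is below 7. Bilirubin and INR have grades of their own, also not given.

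**The case against.** The strongest reply is that coverage exists and only an automatic number is missing. Much of this stands.

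- Section 6.3.1 directs the investigator to decide when less stringent conditions develop. That is a liver-specific instruction, and the conditions it refers to include INR above 1.5.
- Appendix D requires close observation for AST or ALT above 3 × ULN at any baseline, 24-hourly retesting when TBL exceeds 2 × ULN or INR exceeds 1.5, a search for other causes and a hepatology consult. The rise would be seen and acted on with specialist input.
- A related interruption of more than 14 days is itself a permanent stop. The Table 2 hold for other grade 3 events may also apply, although Section 6.2.1.4.2 sends liver laboratory events to Section 6.3.
- Hepatotoxicity that meets SAE criteria is reported within 24 hours. Only the automatic 1-working-day report in Appendix D is unclear, because it refers to the Section 6.3 criteria and 6.3.1 is the only combined one.
- A hold tier in place of an automatic stop is a defensible choice when enzymes were abnormal before treatment.

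The last argument would settle the matter if the hold tier caught the combined signal. It does not: it has no INR trigger and its bilirubin trigger starts at 3 × ULN.

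Two stronger readings are tempting. A reader might infer that these subjects have no liver protection; the provisions above show otherwise. A reader might also infer that any raised baseline enzyme removes a subject from the stop rule. It does not, since the other enzyme can meet it if it began below ULN.

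**Conclusion.** The gap is real but narrow. An eligible subject whose rising enzyme was at or above ULN at baseline cannot meet the hepatic permanent-stop criterion. In the region set out above, such a subject meets no numeric stop or hold trigger. What is missing is an automatic trigger, not all oversight.

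The rule logic follows directly from the text. The size in subjects cannot be given, because the documents do not say how many enter at or above ULN. About 30 of the 45 planned evaluable subjects are in Period 1, where the DLT window covers one treatment week of six; that describes the trial, not the affected group. The conclusion assumes that the entry value serves as baseline and that symptoms, other causes and the remaining withholding triggers are absent. It merits an amendment because the sponsor itself treats the signal as a mandatory stop and the correction is inexpensive.

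**What to change.** 1. **Stop row for baseline ≥ ULN** in Section 6.3.1, Table 2 and Section 6.2.1.4.3: AST or ALT above a sponsor-confirmed multiple of baseline, with TBL > 2 × ULN or INR > 1.5 (not on anticoagulants) and no other cause. An example is > 3 × baseline, capped at 8 × ULN; both numbers are assumptions. The trigger is then min(3 × baseline, 8): 3.0 × ULN at entry 1.0 (continuous with the present row), 3.6 at 1.2, 6.0 at 2.0, and 8.0 from 2.7 upward (3 × 2.7 = 8.1, capped).
2. **Withholding row for smaller rises** in Section 6.3.2 and Table 2, limited to baseline ≥ ULN: AST/ALT > 3 × ULN and increased from baseline, with TBL > 2 × ULN or INR > 1.5 (not on anticoagulants), and no other cause immediately apparent. Entry 2.0 rising to 4 with INR 1.8 would be held (4 < 6.0). Entry 4.0 falling to 3.5 with TBL 2.1 would not. Without these limits the row would also catch falling enzymes and rises explained by CRS or Gilbert's syndrome.
3. **Restart condition for that hold.** Section 6.3.2 allows rechallenge only when another cause is found, so a hold defined by no other cause would have no stated way back.
4. **Appendix D:** state that the 1-working-day report covers the new stop row.
5. **Baseline:** say whether the screening or day 1 value is meant.

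The cost is amendment wording and no added tests, since Appendix D already repeats AST, ALT, bilirubin and INR above 3 × ULN. The downside is that a few raised-baseline subjects are stopped or held by rule rather than by discretion, and a hold in the SC week may make a Period 1 subject non-DLT-evaluable and replaced.

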### 6.3.2 Criteria for Conditional Withholding of Blinatumomab and Other Protocol-required Therapies Due to Potential Hepatotoxicity

For subjects who do not meet the criteria for permanent discontinuation of blinatumomab outlined above and have no underlying liver disease, and eligibility criteria requiring normal transaminases and TBL at baseline or subjects with underlying liver disease and baseline abnormal transaminases, the following rules are recommended for withholding of blinatumomab and other protocol-required therapies:

- Elevation of either AST or ALT according to the following schedule:

Baseline AST or ALT value	AST or ALT elevation
Any	> 8 × ULN at any time
Any	> 5 × ULN but < 8 × ULN for ≥ 2 weeks
Any	> 5 × ULN but < 8 × ULN and unable to adhere to enhanced monitoring schedule
Any	> 3 × ULN with clinical signs or symptoms that are consistent with hepatitis (such as right upper quadrant pain/tenderness, fever, nausea, vomiting, jaundice).

- OR: TBL > 3 × ULN at any time
- OR: ALP > 8 × ULN at any time

Blinatumomab and other protocol-required therapies, as appropriate should be withheld pending investigation into alternative causes of DILI. If IP is withheld, the subject is to be followed according to recommendations in [Appendix D](#) for possible DILI.

Rechallenge may be considered if an alternative cause for impaired liver tests (ALT, AST, ALP) and/or elevated TBL, is discovered and the laboratory abnormalities resolve to normal or baseline ([Section 6.3.3](#)).

